#### 7.2.1. Summary of Treatment-emergent Adverse Events

##### 7.2.1.1. Overall Summary of TEAEs

The overall summary of TEAEs (ie, the AE overview table) will be presented by treatment group and overall, and will include the following events:

- Treatment-emergent adverse events (ie, any TEAE)
- TEAEs leading to study drug discontinuation
- TEAEs related to study drug (ie, treatment related TEAEs)
- TEAEs related to study drug and leading to study drug discontinuation
- Treatment-emergent serious adverse events (ie, any TESAEs)
- TESAEs leading to study drug discontinuation
- TESAEs related to study drug (ie, treatment related TESAEs)
- TESAEs related to study drug and leading to study drug discontinuation
- Deaths

### **7.2.1.2. Specific Summaries of TEAEs**

The number and percentage of subjects with TEAEs will be summarized in 2 ways as follows:

- by SOC and PTs, where the SOCs are ordered alphabetically and PTs within each SOC are sorted in order of decreasing frequency in the overall treatment group. A subject will be counted only once within the same SOC and within the same PT.
- by only PTs, where the PTs are sorted in order of decreasing frequency in the overall treatment group.

A summary of TEAEs by system organ class, preferred term, and severity will also be presented, where each TEAE will be counted under its maximum severity rating only.

The number and percentage of subjects with TEAEs leading to study drug discontinuation, TEAEs related to study drug (ie, treatment related TEAEs), TEAEs related to study drug and leading to study drug discontinuation, TESAEs, TESAEs leading to study drug discontinuation, TESAEs related to study drug (ie, treatment related TESAEs), TESAEs related to study drug and leading to study drug discontinuation, and death will be summarized by SOC and PT. All AEs will be provided in a listing that will include the subject identifier, SOC, PT, and the reported term, date of onset and study day, date of resolution and study day, the seriousness, the severity, the relationship to each individual study drug (for TEAEs), duration, the action taken, and the outcome. All TEAEs will be flagged in the listing. Additionally, subject data listings of deaths, SAEs, AEs leading to study drug discontinuation will be provided.

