## 1. INTRODUCTION

This statistical analysis plan (SAP) describes the planned data analyses and the outputs to be included in the final clinical study report (CSR) for the standalone open-label extension (OLE) Study ATB200-07. The SAP is based on Amendment 3 of the Protocol for Study ATB200-07 dated 10 December 2024.

This final SAP describes the analyses that will be performed for the final CSR for the standalone Study ATB200-07 based on a data cutoff date of 31 December 2024. All data collected through the cutoff date will be reported as summary tables and/or listings.

This SAP has been developed in accordance with Good Clinical Practice (GCP), International Council on Harmonisation (ICH) guideline E9 (Statistical Principles for Clinical Trials), and Amicus standard operating procedure (SOP) ATCRA-SOP-AT-008.

The analyses and statistical methods specified in the final SAP supersede those described in the study protocol.

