## **5.3. Exposure and Treatment Compliance**

Study drug exposure will be summarized for the cipaglucosidase alfa/miglustat combination treatment rather than separately for cipaglucosidase alfa and miglustat. All analyses will be based on the exposure during Study ATB200-07 only.

Analyses will be presented by treatment groups Cipaglucosidase alfa/miglustat–Cipaglucosidase alfa/miglustat, Alglucosidase alfa/placebo–Cipaglucosidase alfa/miglustat, and overall, as defined in Section 4.2. The duration of treatment (ie, extent of exposure), in months, will be calculated as (date of last dose in ATB200-07 – date of first dose in ATB200-07 + 1) / 30.4, and summarized using descriptive statistics (n, mean, SD, median, minimum, and maximum).

In addition, the duration of treatment will be categorized into the exposure intervals below and summarized using number and percentages of subjects:

≤ 3 months, > 3 to ≤ 6 months, > 6 to ≤ 9 months, > 9 to ≤ 12 months, > 12 to ≤ 18 months, > 18 to ≤ 24 months, > 24 to ≤ 36 months, > 36 to ≤ 48 months, > 48 months to ≤ 60 months, and > 60 months.

Additionally, a summary of the duration of treatment (exposure) will be provided by prior ERT status.

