### 6.3. Subgroup Analysis

The following analyses will be provided by visit and by prior ERT subgroups (as defined in Section 4.3.1) with the total.

- Summary of the main efficacy endpoints: 6MWD, % predicted FVC, MMT-lower extremities, PROMIS-Physical Function, PROMIS-Fatigue, and GSGC total score  
In addition, line plots of mean  $\pm$  SE of the change from baseline over time will be provided for the 6MWD and % predicted FVC only.
- Summary of PD endpoints: Hex4 and CK  
In addition, line plots of mean  $\pm$  SE of the change (and percent change) from baseline over time will be provided for the PD endpoints (CK and Hex4).
- Summary of exposure

- Summary of AEs: AE overview, TEAEs by SOC and PT, treatment-emergent serious adverse events (TESAEs) by SOC and PT, IAR overview, and IAR-TEAEs by SOC and PT
- Summary of demographics and baseline characteristics: demography (sex, age at informed consent)
- Summary of disposition: overall disposition table showing populations, number and percentage of subjects discontinuing the study, and reasons for discontinuation

Additional subgroup analyses based on the subsets of subjects defined in Section 4.3.2 will be conducted for the 6MWD and % predicted FVC, as described in Section 4.3.2.

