## 7. ANALYSIS OF SAFETY

### 7.1. Safety Summary Statistics

Safety analyses will be performed on the OLE safety population. Safety data will be summarized using counts (number) and percentages for categorical data. Continuous data will be summarized using descriptive statistics (n, mean, SD, median, Q1, Q3, minimum, and maximum). No formal statistical tests will be performed.

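### The SAP's TEAE, serious TEAE, discontinuation and death tables give numbers and percentages of subjects with no patient-time denominator, although time at risk differs between subjects

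*SAP*

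**What the plan says.** The general rule in SAP 7.1 is "Safety data will be summarized using counts (number) and percentages for categorical data". SAP 7.2.1.1 lists the event types for the overview table and names no other statistic. SAP 7.2.1.2 then says "The number and percentage of subjects with TEAEs will be summarized in 2 ways as follows", with the rule "A subject will be counted only once within the same SOC and within the same PT". It applies number and percentage of subjects to related TEAEs, serious TEAEs, discontinuations and deaths. SAP 6.3 repeats these outputs by prior ERT status: "Summary of AEs: AE overview, TEAEs by SOC and PT".

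Exposure is handled separately. In SAP 5.3, "the duration of treatment will be categorized into the exposure intervals below and summarized using number and percentages of subjects", with bins that begin "≤ 3 months, > 3 to ≤ 6 months, > 6 to ≤ 9 months" and end "> 48 months to ≤ 60 months, and > 60 months". Nothing links those durations to the adverse event tables.

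Time at risk is not common to all subjects. SAP 7.2 counts events up to 30 days after last dose. Under Protocol 8.2, treatment stops when the product is commercialized, is rejected in the subject's country or moves to post-trial access, or when the subject withdraws. Protocol 6.1 says approval has already been given in the EU, Great Britain, the US and other countries.

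Protocol 15.3.4.4 also promises the number of adverse events. SAP 7.2.1 does not carry this over, and SAP 1 gives the SAP precedence.

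For IARs the SAP goes further:
- 7.2.2.3: percentage of infusions with an IAR
- 7.2.2.4: number of IARs per subject and time to first IAR
- 7.2.2.5: event rates over onset intervals up to more than 4 years
- 7.2.2.6: event rates by time after infusion start

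The denominator of the event rates in 7.2.2.5 and 7.2.2.6 is not stated.

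**The concern.** In an extension study the share of subjects who have ever had an event rises with time on study even if the risk never changes. When subjects are followed for different lengths of time, one crude percentage reflects both the rate and the follow-up.

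This bears on the safety question the study exists to answer. A reader of the report could not tell from these tables whether a given percentage of subjects with a serious TEAE is high or low for the time observed. If treatment groups or prior-ERT subgroups differed in follow-up, their percentages could differ for that reason alone. The later addendum (Protocol Appendix 1, 15.3.4) uses only data collected after the database lock, over a period of different length. Crude percentages from the two reports could not be set side by side, whereas rates could.

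**Working it through.** The plan has no figure to reproduce. Protocol 15.2 reports no sample size calculation, and neither document gives an adverse event rate, a dropout rate or an expected exposure distribution. All values of r (first-event rate) and h (dropout hazard) below are assumptions.

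**1. Longest possible exposure.** The original protocol is dated 25 March 2019 (Protocol, Document History). The final report covers the "standalone Study ATB200-07 based on a data cutoff date of 31 December 2024" (SAP 1). A month is 30.4 days (SAP 5.3). From 25 March 2019 to 31 December 2024 inclusive is 2109 days, and 2109 / 30.4 = 69.4 months. This is an outer bound, since no subject could be dosed before the protocol existed.

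**2. Crude percentage at a constant rate r, everyone followed for T years:** 1 − exp(−rT).

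| Assumed r per patient-year | 3 months | 1 year | 5 years |
|---|---|---|---|
| 0.02 | 0.5% | 2.0% | 9.5% |
| 0.10 | 2.5% | 9.5% | 39.3% |
| 0.30 | 7.2% | 25.9% | 77.7% |

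Only the product rT matters in this model: 0.10 for 5 years and 0.20 for 2.5 years both give 39.3%.

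**3. In reverse.** For a crude 30%, r = −ln(0.7)/T. That is 0.357 per patient-year if all were followed for 1 year and 0.071 if all were followed for 5.

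**4. Two groups with the same rate and different dropout.** With dropout hazard h and a cutoff at 5 years, the crude percentage is r/(r+h) × [1 − exp(−5(r+h))] and mean follow-up is [1 − exp(−5h)]/h.

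- r = 0.10, h = 0.05: (0.10/0.15) × [1 − exp(−0.75)] = 35.2%; mean follow-up 4.42 years.
- r = 0.10, h = 0.15: (0.10/0.25) × [1 − exp(−1.25)] = 28.5%; mean follow-up 3.52 years.
- r = 0.10 with the wider contrast h = 0.02 against 0.20: 37.6% against 25.9%.
- A rarer event, r = 0.02, with h = 0.05 against 0.15: 8.4% against 6.7%.
- Equal h in both groups: no gap.

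**5. The proposed rate in the same example.** Mean time at risk to first event or censoring is [1 − exp(−5(r+h))]/(r+h). For r = 0.10 this is 3.52 years at h = 0.05 and 2.85 years at h = 0.15. Then 0.352/3.52 and 0.285/2.85 both equal 0.10, or 10 per 100 patient-years, so the artefact disappears.

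**The case against.** The study has no control group and plans no safety test (Protocol 8.6, SAP 7.1). Both groups come from the same parent study, receive the same drug and share one cutoff, so follow-up may turn out similar. The percentage of subjects ever affected is a legitimate descriptive summary. Exposure is tabulated by the same treatment groups and by prior ERT status, so a reader can see whether follow-up differs. A reader could even divide by number of subjects times mean exposure. In the example in step 4 that gives 35.2/4.42 = 8.0 and 28.5/3.52 = 8.1 per 100 patient-years, which removes nearly all of the false gap.

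Much of this stands, and it limits the point to the absence of a rate. It does not remove it. Descriptive status does not make a percentage over variable follow-up easier to interpret. The hand calculation also understates the assumed rate of 10, because it counts time after the first event, and the correct time at risk for each event type cannot be recovered from the planned tables.

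A reader might go further and infer that every adverse event table is crude. SAP 7.2.2.3 to 7.2.2.6 contradict that. Infusions administered are a natural denominator for an infusion reaction, and rates by onset interval are more informative about IARs than one pooled rate. A reader might also take the exposure bins to mean that exposure really runs from under 3 to over 60 months. They are reporting categories, and any of them may be nearly empty.

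**Conclusion.** The point holds for the general TEAE tables. SAP 7.2.1 and its prior-ERT versions in 6.3 report subjects without time, while the design lets time at risk vary by country and by withdrawal. Under a constant rate, the same underlying risk of 0.1 per patient-year appears as anything from 2.5% at 3 months to 39.3% at 5 years.

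Those sizes rest on assumed rates, assumed dropout hazards and a constant hazard. It would be tempting to conclude that the planned group comparison is distorted, but the documents do not support that: distortion between groups needs unequal follow-up, and nothing in them shows it. What they show is a primary safety summary that cannot be read as a rate. IARs are partly covered; the gap there is the unstated denominator of the event rates.

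**What to change.** - In the AE overview, the serious TEAE table and the table of most frequent preferred terms, add subjects with a first event per 100 patient-years at risk beside the crude counts. Censor time at the first event or the end of the TEAE period. Show the rate by treatment group, overall and by prior-ERT subgroup.
- In SAP 7.2.2.5, state that the event rate in each onset interval is events divided by the patient-years accrued in that interval. The intervals run from 3 days to a year or more, and that analysis is meant to show whether IARs fade or appear late.

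The dose and onset dates needed are already used in SAP 4.4.1, 5.3 and 7.2.1.2, so no new data are required. The cost is a few columns in existing tables and a footnote that a single rate assumes a roughly constant hazard.

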### **7.2.2. TEAEs Reported as Infusion-associated Reactions**

For any AE, the reporting investigator is requested to enter on the AE eCRF whether the AE is deemed to be an infusion-associated reaction (IAR) and determine the relationship to each of the study drug components.

#### **7.2.2.1. Overall Summary of TEAEs Reported to be IAR**

An overall summary table of TEAEs reported to be IARs (ie, IAR-TEAEs) will be provided. This IAR overview table will present the number and percentage of subjects who had: any IAR-TEAE; any IAR-TEAE leading to study drug discontinuation; any IAR-TESAE; any IAR-TESAE leading to study drug discontinuation; and any IAR-TEAE leading to death).

#### **7.2.2.2. Specific Summaries of IAR-TEAEs**

To further characterize TEAEs considered by the reporting investigator to be IARs, specific summaries of TEAEs reported as IARs will be provided, where feasible. That is, the number and percentage of subjects who experienced any IAR-TEAEs, IAR-TEAE leading to study drug discontinuation, IAR-TESAE, IAR-TESAE leading to study drug discontinuation, and IAR-TEAE leading to death will be presented by SOC and PT within each SOC, and by treatment group and overall. A subject will be counted only once within the same SOC and within the same PT. A summary of IAR-TEAEs will also be presented by severity (mild, moderate, severe) and by relationship to each treatment component (ciphaglucosidase alfa and miglustat) as well as for the combination treatment (ciphaglucosidase alfa/miglustat).

Listings of treatment-emergent IAR-TEAEs, serious IAR-TEAEs, IAR-TEAEs leading to study drug discontinuation, and IAR-TEAE related deaths will be provided.

### **7.2.2.3. Summary of Infusions and IARs for All Subjects and for Subjects with IARs**

A summary of total infusions and infusions associated with IARs will be provided for all subjects as well as for subjects with IARs. This summary will include the following:

- Summary for all subjects:
  - Overall total number of infusions administered during ATB200-07
  - Overall total number of infusions associated with IARs
  - Overall percentage of infusions associated with IARs, where the percentage is calculated as: total number of infusions associated with IARs / total number of infusions administered
- Summary for subjects with IARs:
  - Total number of infusions in subjects with IARs
  - Number of infusions associated with IARs in subjects with IARs
  - Percentage of infusions associated with IARs in subjects with IARs, where the percentage is calculated as: total number of infusions associated with IARs in subjects with IARs / total number of infusions in subjects with IARs

For this summary, any infusion suspected by the reporting investigator as leading to an IAR is considered an ‘infusion associated with IAR.’

### **7.2.2.4. Analysis of Subjects with IARs and Time to First IAR-TEAE**

For subjects with IAR-TEAEs, a summary table will be provided displaying the following:

- Summary of IAR-TEAEs by subjects with IARs:
  - the number and percentage of subjects with IAR-TEAEs
  - total number of IAR-TEAEs
  - the number of subjects who experienced 1, 2, 3, 4 to 6, 7 to 10, 11 to 19, and  $\geq 20$  IARs in each treatment group and overall
- Time to first IAR-TEAE for subjects with IARs:
  - the time (in weeks) from the first dose of study drug to the onset of the first TEAE that is an IAR (ie, IAR-TEAE) will be calculated for each subject as:  
$$\text{Time to first IAR-TEAE (Weeks)} = (\text{date of the first IAR-TEAE} - \text{date of first dose of study drug in ATB200-07} + 1) / 7.$$
  - The calculated times will be summarized as a continuous variable and included in the same table.

In addition, a listing displaying the number of infusions and infusions that were associated with IARs by each individual subject who had an IAR will be provided. For each subject, this listing

includes subject ID, whether or not pre-infusion medication was given, number of infusions received, number of infusions that were associated with IARs, percentage of infusions associated with IARs, a chronological listing of the number of IARs corresponding to (or associated with) each infusion, and time to first IAR.

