#### **7.2.2.5. Analysis of IARs by Onset Intervals**

The IARs will also be analyzed by onset intervals categorized as follows:

- 1 to 3 days, 4 to 7 days, 8 to 14 days, 15 to 28 days, 29 days to  $\leq$  3 months, > 3 months to  $\leq$  6 months, > 6 months to  $\leq$  12 months, > 12 months to  $\leq$  2 years, > 2 years to  $\leq$  3 years, > 3 years to  $\leq$  4 years, and > 4 years.

The event rates and changes in severity over time (over these intervals) will be summarized for each treatment group. This analysis will further describe the clinical characteristics of IARs and help determine whether the IARs disappear over time or appear late.

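### Time to first IAR is summarised only in subjects who had one, with no censoring, so it says little about IAR risk; a cumulative-incidence estimate should be added

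*SAP*

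**What the plan says.** SAP 7.2.2.4 introduces the item as "Time to first IAR-TEAE for subjects with IARs". For each such subject the time in weeks is (date of first IAR-TEAE − date of first dose in ATB200-07 + 1) / 7. The instruction for reporting is "The calculated times will be summarized as a continuous variable and included in the same table". SAP 7.1 defines that kind of summary for safety data: "Continuous data will be summarized using descriptive statistics (n, mean, SD, median, Q1, Q3, minimum, and maximum").

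The section mentions no censoring. Neither the SAP nor the protocol plans a Kaplan-Meier or other cumulative-incidence estimate of first IAR.

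The plan does report IAR risk in other ways:
- The same table gives "the number and percentage of subjects with IAR-TEAEs".
- SAP 7.2.2.1 and 7.2.2.2 count subjects with IARs overall and by SOC and PT.
- SAP 7.2.2.3 gives the percentage of all administered infusions that were associated with an IAR.
- SAP 7.2.2.5 divides IARs by onset interval, from the first 3 days to beyond 4 years, and says "The event rates and changes in severity over time (over these intervals) will be summarized for each treatment group". It does not state the denominator of those rates. Its stated aim is to learn whether IARs fade with time or appear late.

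Follow-up ends at a calendar date, "based on a data cutoff date of 31 December 2024" (SAP 1), or earlier if the subject leaves. SAP 4.2 presents results for the group continuing cipaglucosidase alfa/miglustat, the group switched from alglucosidase alfa/placebo, and both combined.

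**The concern.** Time to first IAR is right-censored: a subject who reached the cutoff or left without an IAR is known only to have a time longer than that follow-up. A mean or median over the observed times alone describes when IARs occurred among affected subjects, given that they occurred before follow-up ended. It does not describe how soon, or how likely, a treated subject is to have one.

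The practical risk is misreading. The two treatment groups differ in a way that makes first-IAR timing interesting: one has already had the drug in ATB200-03, while the other meets it on Day 1. A reader will compare their times to first IAR. Groups with quite different risk could show nearly the same figure. Under some hazard shapes, groups with the same risk but different follow-up could show different figures.

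**Working it through.** The documents give no IAR rate, no expected time to first IAR and no hazard shape, so there is no planned figure to reproduce. The check computes what the SAP would report, the mean time among subjects whose first IAR falls within follow-up τ, under stated assumptions.

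**Inputs**
- From the SAP: events-only summary (7.2.2.4); last visit window Week 234 (4.5); about 110 subjects at most (3.3).
- Assumed: cumulative risk p of 10% to 80% at 234 weeks; τ of 234 or 117 weeks, the same for all subjects; three families of hazard.

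**Constant hazard.** With λ = −ln(1 − p)/234, the reported mean is E[T | T ≤ τ] = 1/λ − τ/(exp(λτ) − 1).
- p = 10%: λ = 0.10536/234, so 1/λ = 2221 weeks; 234/(1/0.9 − 1) = 2106; mean = 114.9 weeks.
- p = 40%: 1/λ = 458; 234/(1/0.6 − 1) = 351; mean = 107.1 weeks.
- p = 80%: mean = 86.9 weeks.
- p = 10% hazard, τ halved to 117: mean = 58.0 weeks.

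A fourfold rise in risk (10% to 40%) moves the mean by 7%, although the true mean time falls from 2221 to 458 weeks. Halving follow-up at unchanged risk moves it by 50%.

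**Falling hazard.** Weibull, F(t) = 1 − exp(−L(t/234)^k) with L = −ln(1 − p), and mean = τ − ∫₀^τ F(t)dt / F(τ), integrated numerically.

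**Early clustering.** A share of subjects is susceptible, with exponential onset of mean m. The constant-hazard formula then applies with λ = 1/m, and the susceptible share cancels out.

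| Model | 10% risk, τ = 234 | 40% risk, τ = 234 | Change with risk | 10% risk, τ = 117 | Change with follow-up |
|---|---|---|---|---|---|
| Constant | 114.9 | 107.1 | −7% | 58.0 | −50% |
| Weibull k = 0.7 | 94.2 | 86.2 | −9% | 47.5 | −50% |
| Weibull k = 0.5 | 76.0 | 68.3 | −10% | 38.3 | −50% |
| Weibull k = 0.3 | 52.2 | 45.7 | −12.5% | 26.3 | −50% |
| Clustered, m = 8 | 8.0 | 8.0 | 0% | 8.0 | 0% |
| Clustered, m = 26 | 26.0 | 26.0 | 0% | 24.7 | −5% |
| Clustered, m = 52 | 49.4 | 49.4 | 0% | 38.2 | −23% |

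Means are in weeks. In the clustered rows, 10% and 40% are the susceptible shares.

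**Limit of the insensitivity.** At 80% risk the mean does respond: compared with 10% risk it is 24% lower under a constant hazard (86.9 against 114.9) and 42% lower at k = 0.3 (30.4 against 52.2).

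**Sampling noise.** In 20,000 simulated studies of 110 subjects with constant hazard, the SD of the events-only mean was 21.4 weeks at 10% risk and 10.2 at 40%. The 7.8-week difference between those risks is smaller than either SD.

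**With IAR-free subjects kept.** With 110 subjects and no early censoring, cumulative incidence at 234 weeks would be 10% (SE √(0.1 × 0.9/110) = 2.9 points) against 40% (SE √(0.4 × 0.6/110) = 4.7 points). These are the same two risks that gave 114.9 and 107.1 weeks.

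**The case against.** The best defence is that the plan does not lose IAR risk. The percentage of subjects with IARs stands in the same table, so 10% against 40% would be visible beside the two similar times. SAP 7.2.2.3 gives an infusion-based percentage over all subjects, and 7.2.2.5 looks at onset over time. The row is also openly conditional: the section title, lead-in and bullet all refer to subjects with IARs. Onset time among affected subjects is a legitimate description, and no test or sample size depends on it.

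Most of this stands, and it limits the point. What remains is that none of these displays gives first-IAR timing with a risk set. The percentage of subjects carries no time and takes no account of unequal follow-up. The infusion percentage has no time axis. The onset-interval rates cover all IARs and state no denominator.

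Three stronger readings are tempting, but the documents do not support them:
- A reader might infer that the statistic mainly reflects length of follow-up. That needs a constant or slowly falling hazard. With onset averaging 8 weeks in susceptible subjects, halving follow-up changes nothing. The documents give no hazard shape, although the monitoring after the first three infusions (protocol 12.2.2) and the fine early bins in SAP 7.2.2.5 show attention to early onset.
- A reader might take the exposure categories in SAP 5.3, which end "> 48 months to ≤ 60 months, and > 60 months", as the range of follow-up. They are display bins; the distribution of follow-up is not reported.
- A reader might treat first-IAR timing as a listed endpoint. SAP 2.3.1 lists frequency and severity of immediate and late IARs. Early and late there refer to time since the infusion (protocol 13.1.3), not time since first dose.

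**Conclusion.** The point holds in a limited form and is worth acting on. The planned summary omits IAR-free subjects, and no censored estimate of first-IAR timing replaces it. Up to about 40% cumulative risk, a fourfold difference in risk moves the mean by 0% to about 12.5% under every hazard shape tried; at very high risk it responds more. Dependence on follow-up ranges from none (clustering at 8 weeks) to proportional (constant or slowly falling hazard), and which applies cannot be settled from the documents.

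The risks, follow-up lengths and hazard shapes are assumptions, not trial figures. The consequence is confined to how first-IAR timing is read, overall and between the continuing and switched groups. Reporting of IAR frequency and severity is not undermined.

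**What to change.** Add to SAP 7.2.2.4 a Kaplan-Meier cumulative incidence of first IAR-TEAE in all OLE-SAF subjects, by treatment group and overall. Censor IAR-free subjects at the earlier of last dose + 30 days, which matches the treatment-emergent period in SAP 7.2, and the data cutoff. Report estimates, 95% CIs and numbers at risk at 3, 12, 24, 36 and 48 months, with a plot.

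The existing summary need not be deleted. If it is kept, label it in the table: among subjects with an IAR; not an estimate of risk.

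The cost is one extra table, one figure and a short change to the SAP text. The dates needed are already used for exposure and for the current calculation, so no new data and no protocol change are required. The addition also serves the aim stated in SAP 7.2.2.5 of seeing whether IARs disappear or appear late.
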